8. STUDY ASSESSMENTS AND PROCEDURES

8.1. Administrative and Baseline Procedures

The investigator (or an appropriate delegate at the investigator site) must obtain a signed and dated ICD before performing any study-specific procedures.

Study procedures and their timing are summarized in the SoA. Protocol waivers or exemptions are not allowed.

Adherence to the study design requirements, including those specified in the SoA, is essential and required for study conduct.

All screening evaluations must be completed and reviewed to confirm that potential participants meet all eligibility criteria. The investigator will maintain a screening log to record details of all participants screened and to confirm eligibility or record reasons for screening failure, as applicable.

Every effort should be made to ensure that protocol-required tests and procedures are completed as described. However, it is anticipated that from time to time there may be circumstances outside the control of the investigator that make it unfeasible to perform the test. In these cases, the investigator must take all steps necessary to ensure the safety and well-being of the participant. When a protocol-required test cannot be performed, the investigator will document the reason for the missed test and any corrective and preventive actions that they have taken to ensure that required processes are adhered to as soon as possible. The study team must be informed of these incidents in a timely manner.

Part A only:

A participant who qualified for this protocol but did not enroll from an earlier cohort/group may be used in a subsequent cohort/group without rescreening, provided laboratory results obtained prior to the first dose administration meet eligibility criteria for this study. In addition, other clinical assessments or specimen collections, eg, retained research samples, may not need to be repeated, as appropriate.

Part B only:

Participants will be screened within 35 days prior to administration of the study intervention to confirm that they meet the study population criteria for the study. If the time between Screening and dosing exceeds 35 days as a result of unexpected delays (eg, delayed drug shipment), then participants do not require rescreening if the laboratory results obtained prior to first dose administration meet eligibility criteria.

Parts A and B:

Laboratory, analyte results (eg, PK, NT-proBNP, target engagement) that have been collected for the purposes of this study and could unblind the study will not be reported to investigative sites or other blinded personnel until after the study has been unblinded.

For samples being collected and shipped, detailed collection, processing, storage, and shipment instructions and contact information will be provided to the investigator site prior to initiation of the study.

The total blood sampling volume for individual participants in this study is approximately 180 mL for Part A and 390 mL for Part B. The actual collection times of blood sampling may change. Additional blood samples may be taken for safety assessments at times specified by Pfizer, provided the total volume taken during the study does not exceed 550 mL during any period of 56 consecutive days.

To prepare for study participation, participants will be instructed on the information in the Lifestyle Considerations and Concomitant Therapy sections of the protocol.

8.1.1. Spirometry

Spirometry, if necessary, will be performed prior to randomization, after the participant has met all other inclusion / exclusion criteria (except those obtained by 6MWT and RHC). It must be performed by trained personnel using standard equipment and techniques in accordance with current ERS/ATS guidelines for measurement of lung volume and interpreted using relevant standard reference values. Data from the spirometry testing will be used to assess eligibility criteria and kept as source documentation. If spirometry is not necessary, historical evidence of the participant's meeting lung function eligibility requirements should be documented in source. performed as part of the participant's usual medical care or as part of the diagnostic assessment of PAH within 1 year of Screening may be used to assess eligibility, provided such data are available in source documentation.

8.2. Efficacy Assessments (Part B only)

Planned time points for all exploratory PD and efficacy assessments are provided in the SoA.

8.2.1. Pulmonary Vascular Resistance by Right Heart Catheterization

Pulmonary vascular resistance (PVR) will be measured by right heart catheterization (RHC) during the Screening period and at the Week 24 visit in accordance with the site's/investigators standard practice (SOPs). The RHC should be performed after confirmation of all other eligibility criteria and within 2 weeks of randomization. The RHC may be performed within -10 to + 5 days of the Week 24 visit. Data from RHC performed as part of the participant's usual medical care or as part of the diagnostic assessment of PAH within 12 weeks of signing the ICD may be used to assess eligibility, provided required data are available for entry into the CRF.

In addition to PVR, the RHC will also assess the following hemodynamic variables:

- RAP, mean PAP, mean PCWP / PAOP, RV SBP, RV DBP, HR
- CO is measured in triplicate either by the Fick method or by the thermodilution method. The same method is to be used at the Screening and Week 24 or ED visits.

These hemodynamic parameters are to be assessed when the participant is at a stable hemodynamic rest state which is defined as 3 consecutive mean PAP and CO measurements within 10% of each other.

PVR is to be calculated and entered in the CRF.

The acquired RHC data, as available, may be reviewed centrally to confirm pulmonary vascular hemodynamic measurements. If performed, details of the central review will be provided separately.

8.2.2. 6-Minute Walk Test

The 6MWT is a submaximal exercise test that entails measurement of distance walked over a span of 6 minutes.¹⁸ The 6MWD (distance traveled in meters) provides a measure for integrated global response of multiple cardiopulmonary and musculoskeletal systems involved in exercise. The 6MWT should be performed in accordance with the PI's usual procedure. The 6MWT is to be performed at least twice during the Screening Period at least 4 hours (but no longer than 1 week) apart and distances must be within 15% of each other, calculated from the higher number. The 6MWT is to be performed at Screening, and as additional time points per SoA. If occurring on the same day, 6MWT should be performed before RHC. Detailed instructions on conducting the 6MWT will be provided separately.

The Borg CR10 scale® will be completed before and after each 6MWT as specified in the SoA. (See Section 8.2.4.6.)

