Visit Window			±1 day	±2 days	±2 days	±2	±2 days	±2 days	±2 Days		 All screening should be done ≤35 days before the first dose. A delay in randomization ≤ 7 days due to the need to acquire RHC, PFT and /or repeat laboratory data will not be considered as a PD. See Section 8.4.3 for follow-up AE and SAE assessments.
											 RHC. Pre- randomization RHC should be done within 2 weeks of randomization. Data from a RHC performed within 12 weeks of Screening as part of the participant's usual disease monitoring may satisfy this requirement provided all required data are available. The EOT RHC may be performed within -10 /

Visit Identifier Abbreviations used in this table may be found in Appendix10.							Trea	itment	Period	Early Discontinuation	Notes
Days relative to Day 1	Screen (Up to 35 days before Day 1)	Day 1	Day 8	Day 29	Day 57	Day 85	Day 113	Day 141	Day 169		• Day relative to start of study intervention (Day 1).
			Week 1	Week 4	Week 8	Week 12	Week 16	Week 20	Week 24 / EOT		
Visit Window			±1 day	±2 days	±2 days	±2 days	±2 days	±2 days	±2 Days		 All screening should be done ≤35 days before the first dose. A delay in randomization ≤ 7 days due to the need to acquire RHC, PFT and /or repeat laboratory data will not be considered as a PD. See Section 8.4.3 for follow-up AE and SAE assessments.
											+5 days of the nominal Week 24 visit.See Section 8.2.1 for additional information.
Contraception check	Х	Х	Х	Х	Х	Х	Х	Х	Х	Х	

Visit Identifier Abbreviations used in this table may be found in Appendix10.							Trea	atment	Period	Early Discontinuation	Notes
Days relative to Day 1	Screen (Up to 35 days before Day 1)		8	Day 29	Day 57	Day 85	Day 113	Day 141	Day 169		• Day relative to start of study intervention (Day 1).
			Week 1	Week 4	Week 8	Week 12	Week 16	Week 20	Week 24 / EOT		
Visit Window Laboratory Assessments			±1 day	±2 days	±2 days	±2 days	±2 days	±2 days	±2 Days		 All screening should be done ≤35 days before the first dose. A delay in randomization ≤ 7 days due to the need to acquire RHC, PFT and /or repeat laboratory data will not be considered as a PD. See Section 8.4.3 for follow-up AE and SAE assessments. See Section 8.3.5 for
											 additional information. See Appendix 2 for a list of Clinical Laboratory tests to be done. For laboratory collection volumes, see the laboratory manual.

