6.4.4. Sensitive Clinical Data

Sensitive clinical data are data collected in this study that have the potential to unblind a participant's treatment assignment. Access to sensitive clinical data will be restricted to authorized individuals until the study has been unblinded. The following data variables are considered sensitive clinical data:

- Target engagement biomarker (after randomization)
- NT-proBNP (after randomization)

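### The rule that the walk test precedes the Week 24 catheterization applies only on the same day, so Week 24 6MWD, WHO class and PROs can be collected after the site knows the haemodynamic result

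*Protocol*

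**What the plan says.** **Timing.** Section 8.2.1 of the protocol states: "The RHC may be performed within -10 to + 5 days of the Week 24 visit". The Part B Schedule of Activities (SoA, Table 3) gives the same limits, but counts from the nominal visit: "The EOT RHC may be performed within -10" days, up to plus "5 days of the nominal Week 24 visit". The SoA places the 6MWT, Borg scale, WHO class and PROs at the Week 24 visit itself (Day 169, plus or minus 2 days).

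**Order.** Section 8.2.2 has one rule linking the two procedures: "If occurring on the same day, 6MWT should be performed before RHC". Section 8.2.3 sets no order for WHO class. Section 8.2.4 asks for PROs before the participant has had much contact with site staff, and does not mention the RHC.

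**Access to the result.** Under Section 8.2.1 the RHC follows the site's own standard practice, and "PVR is to be calculated and entered in the CRF". Central reading is optional: "The acquired RHC data, as available, may be reviewed centrally to confirm pulmonary vascular hemodynamic measurements". In Section 6.4.4, the list introduced by "The following data variables are considered sensitive clinical data" has two entries, the target engagement biomarker and NT-proBNP, both after randomization. Section 8.1 withholds from sites "Laboratory, analyte results (eg, PK, NT-proBNP, target engagement) that have been collected for the purposes of this study and could unblind the study". Neither provision covers RHC data.

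**The concern.** Section 4.2.2 hypothesises that the drug lowers pulmonary vascular resistance (PVR). If it does, the Week 24 RHC result will tend to be better on active treatment than on placebo. Staff who know that result before they supervise the walk, grade WHO class or talk to the participant may encourage or grade differently. A participant who knows it may walk harder or rate symptoms differently. Because the knowledge would differ by arm, the error would be directional, not random.

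The measures at stake depend on effort or judgement: Week 24 6MWD (a secondary endpoint in Section 3.2), the Borg scale and other PROs (exploratory, including PGI-C, which asks about change since starting study medication), and WHO class. WHO class and 6MWD also enter the definition of clinical worsening in Section 8.3.12.

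**Working it through.** There is no plan figure to reproduce. The check is day arithmetic plus a comparison of provisions.

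**1. Windows in study days (SoA anchor, nominal Day 169).**
- RHC: 169 − 10 = 159 to 169 + 5 = 174, which is 16 permitted days.
- Week 24 visit: 169 − 2 = 167 to 169 + 2 = 171, which is 5 permitted days.
- RHC days before the whole visit window: 159 to 166 = 8. Overlapping it: 167 to 171 = 5. After it: 172 to 174 = 3. Total 8 + 5 + 3 = 16.

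**2. Longest lead of RHC over the visit.**
- Counted from the actual visit (Section 8.2.1): 10 days.
- Counted from the nominal visit (SoA): 171 − 159 = 12 days.

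**3. Reach of the order rule.** Relative to the visit, the permitted offsets are −10 to +5, or 16 values. The same-day rule governs offset 0 only, and only for the 6MWT. Ten offsets (−10 to −1) put the RHC first with no rule. Five (+1 to +5) put it after the visit, where the problem does not arise.

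**4. Open-label extension (OLE) entrants.** Section 4.1.2 has them enter the OLE after all Week 24 activities are complete and receive the first OLE dose at the Week 24 visit. Read literally, their RHC must be done by that visit, leaving offsets −10 to 0, or 11 values. Ten of the 11 have no order rule. Early catheterization is therefore a normal path for this group.

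**5. Who can know the result.** The site performs the procedure and PVR is recorded in the CRF, so site knowledge follows from the text. Participant knowledge is neither stated nor barred.

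**6. Internal comparison.** Section 4.2.2 expects NT-proBNP to fall as a consequence of improved pulmonary vascular and right ventricular haemodynamics. Section 6.4.4 restricts NT-proBNP as potentially unblinding but leaves the haemodynamic measurement itself unrestricted.

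**7. Size.** A spurious arm difference in 6MWD would be roughly E × w × k × (pA − pP). E is the shift in metres between those known to have improved and those known not to have. The share with RHC before the walk is w, and k is the share of those whose result is known to the tester or participant. The proportions with improved PVR in each arm are pA and pP. The protocol gives none of these, so no figure in metres can be derived.

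**The case against.** The case on the other side has real substance.

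- **Disclosure.** A reader might infer that participants are told their RHC result before they walk and fill in questionnaires. The protocol does not say so. It only fails to prevent it, so the participant part of the argument is conditional.
- **Blinding.** A reader might infer that the trial is unblinded. It is not: Sections 6.4.1 to 6.4.3 keep participants, site staff and the sponsor staff running the study blind to assignment. One patient's PVR change does not reveal an allocation, and leaving RHC data off the Section 6.4.4 list is a judgement that contradicts nothing.
- **Primary endpoint.** A reader might extend the worry to NT-proBNP. It is a laboratory value withheld from sites and does not depend on effort or expectation, so this mechanism does not touch it.
- **Existing safeguards.** The PRO rule in Section 8.2.4 guards against influence at the visit, and Section 8.2.2 promises separate 6MWT instructions that might set an order across days. The first does not reach an RHC done days earlier. The second cannot be seen, and the only order rule stated in the protocol is the same-day one.
- **Importance.** This is a trial of about 36 participants. The hypothesis in Section 9.1.2 concerns NT-proBNP only, and 6MWD has no estimand of its own. Section 4.2.2 even calls 6MWD exploratory. A catheterization window is also a reasonable feasibility choice.

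These points limit the weight of the concern. They do not remove the gap: a site that follows the protocol exactly can collect these endpoints after seeing a result expected to differ by arm.

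**Conclusion.** The point holds as a cheap improvement. The stated window and the same-day rule together allow Week 24 6MWD, Borg, WHO class and PROs to be collected after the site knows the haemodynamic result, by up to 10 days (12 under the SoA anchor). The consequence is a risk of expectation bias or partial functional unblinding in one secondary endpoint and several exploratory ones.

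Its size cannot be estimated from the protocol. It depends on how often the early window is used, who learns the result, and how far PVR separates the arms. It is zero if nobody involved in the assessments knows the result. A later comparison of participants by order of RHC and walk would not settle the matter, because that order is not randomized.

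**What to change.** Extend the existing order rule from the same day to the whole window. In Sections 8.2.1 and 8.2.2, with a matching SoA note, require the Week 24 PROs, WHO class and 6MWT/Borg to be completed before the Week 24 RHC whatever the day. Allow these assessments to move forward within the RHC window when the RHC is done early, as it will be for OLE entrants. Use one anchor, actual or nominal Week 24 visit, in both places. Availability of RHC results for patient care stays as it is.

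The cost is one sentence, one SoA note and tighter scheduling, with no added procedure. Some Week 24 walk tests and PROs would be taken a few days early, at the extreme 10 days before nominal Day 169, which is already accepted for PVR.

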8.2.3. WHO Functional Class Assessments

The WHO class system is used to provide information about how affected an individual is by their disease according to 4 functional classes that are detailed in the table below. The WHO functional assessment is to be completed as per the SoA for Part B.

WHO Class	Description
Class I	Patients with PH but without resulting limitation of physical activity.
	Ordinary physical activity does not cause undue dyspnea or fatigue,
	chest pain, or near syncope.
Class II	Patients with PH resulting in a slight limitation of physical activity.
	They are comfortable at rest. Ordinary physical activity causes undue
	dyspnea or fatigue, chest pain, or near syncope.
Class III	Patients with PH resulting in marked limitation of physical activity.
	They are comfortable at rest. Less than ordinary activity causes undue
	dyspnea or fatigue, chest pain, or near syncope.
Class IV	Patients with PH with inability to carry out any physical activity without
	symptoms. These patients manifest signs of right heart failure. Dyspnea
	and/or fatigue may even be present at rest. Discomfort is increased by
	any physical activity.

WHO Functional	Class Assessment for Pulmonary	y Arterial Hypertension

8.2.4. Quality of Life Assessments

PROs are administered at timepoints as specified in the SoA and should be collected before the participant has had significant interactions with site personnel with the exception of the Borg CR 10 scale® which is to be completed before and after each 6MWT (See Section 8.2.4.6.)

8.2.4.1. SF-36 assessment

The 36-Item Short Form Survey (SF-36) is an outcome measure instrument for the objective measure of the quality of life. It comprises 36 questions that cover eight domains of health:

1) Limitations in physical activities because of health problems.

2) Limitations in social activities because of physical or emotional problems

3) Limitations in usual role activities because of physical health problems

4) Bodily pain

5) General mental health (psychological distress and well-being)

6) Limitations in usual role activities because of emotional problems

7) Vitality (energy and fatigue)

8) General health perceptions

8.2.4.2. EQ-5D-5L

The EQ-5D-5L is a self-assessed, health-related, quality of life questionnaire. The scale measures quality of life on a 5-component scale including mobility, self-care, usual activities, pain/discomfort, and anxiety/depression. Each level is rated on a scale that describes the degree of problems in that area (ie, I have no problems walking about, slight problems, moderate problems, severe problems, or unable to walk). This tool also has an overall health scale where the rater selects a number between 0-100 to describe the condition of their health, 100 being the best imaginable.

8.2.4.3. PAH-SYMPACT

A multi-domain PRO that includes assessments of cardiopulmonary, cognitive/emotional and physical impact symptoms.

8.2.4.4. PGI-S

The Patient Global Impression of Severity (PGI-S) consists of 1 question that asks the participant to evaluate the severity of their PAH symptoms over the past 7 days, on a 5-point verbal response scale that ranges from "None" to "Very Severe".

8.2.4.5. PGI-C

The Patient Global Impression of Change (PGI-C) consists of 1 question that asks the participant to evaluate the change in the severity of their PAH symptoms since the start of the study medication, on a 5-point verbal response scale that ranges from "much better" to "much worse".

8.2.4.6. Borg CR10 scale®

This scale is used to assess the perceived exertion and fatigue, breathlessness and difficulties breathing (dyspnea). The scale will be completed before and after each 6MWT as specified in the SoA.

8.3. Safety Assessments

Planned time points for all safety assessments are provided in the SoA. Unscheduled safety measurements may be obtained at any time during the study to assess any perceived safety issues.

If multiple procedures are scheduled at the same time, vital signs (BP, pulse, RR) and ECGs should be done before collection of blood specimens.

8.3.1. PEs

A complete PE is to be performed at Screening and brief PE is to be performed at all other visits as per the SoAs.

A complete PE will include, at a minimum, assessments of the cardiovascular, respiratory, gastrointestinal, skin, and neurological systems.

A brief PE will be focused on general appearance, skin, and the respiratory and cardiovascular systems, and as guided by participant-reported symptoms.

PEs may be conducted by a physician, trained physician's assistant, or nurse practitioner as acceptable according to local regulation.

Height will be measured and recorded in cm and accuracy to the nearest 0.1 cm at the Screening visit only. Body weight will be measured as per the SoAs, in kg, and accuracy to the nearest 0.1 kg. For measuring weight, a scale with appropriate range and resolution is used and must be placed on a stable, flat surface. Participants must remove shoes, bulky layers of clothing, and jackets so that only light clothing remains. They must also remove the contents of their pockets and remain still during measurement of weight.

Investigators should pay special attention to clinical signs related to previous serious illnesses.

PE findings collected during the study will be considered source record and will not be required to be reported, unless otherwise noted. Any untoward PE findings that are identified during the active collection period and meet the definition of an AE or SAE (Appendix 3) must be reported according to the processes in Sections 8.4.1 to 8.4.3.

For Part B, any physical exam findings related to the participant's underlying disease, and any chronic skin lesions should be recorded in the Past Medical History CRF.

8.3.2. Vital Signs

Any untoward vital sign findings that are identified during the active collection period and meet the definition of an AE or SAE (Appendix 3) must be reported according to the processes in Sections 8.4.1 to 8.4.3.

8.3.2.1. Blood Pressure and Pulse Rate

BP and PR measurements will be assessed with a completely automated device. Manual techniques will be used only if an automated device is not available.

Sitting or semi-recumbent BP and PR will be measured with the participant's arm supported at the level of the heart with feet flat on the floor and back supported and recorded to the nearest mm Hg after approximately 5 minutes of rest in a quiet setting without distractions. The same arm (preferably the dominant arm) will be used throughout the study. Participants should be instructed not to speak during measurements. The same position should be used for all assessments for a given participant.

The same properly sized and calibrated BP cuff will be used to measure BP each time. The use of an automated device for measuring BP and PR is acceptable; however, when done manually, PR will be measured in the brachial/radial artery for at least 30 seconds. When the timing of these measurements coincides with a blood collection, BP and PR should be obtained prior to the nominal time of the blood collection.

Additional collection times, or changes to collection times, of BP and PR will be permitted, as necessary, to ensure appropriate collection of safety data.

